## **I. SPECIFIC AIMS**

**Specific Aim 1:** To develop a patient navigator (PN) program for lung screening for patients who are current smokers, aged 55-77 years, potentially eligible for lung screening and are receiving care at community health centers (CHCs) affiliated with MGH.

**Specific Aim 2:** To evaluate the effectiveness of the new lung screening PN program in improving screening rates and increasing use of tobacco cessation services in a randomized controlled trial.

**Specific Aim 3:** To demonstrate that equity is maintained in rates of lung screening and in follow up of abnormal chest CT results, comparing eligible smokers from CHCs with eligible smokers from other practices within the MGH primary care network.

**Specific Aim 4:** To collect quantitative data about patient satisfaction with the navigators in the lung screening PN program

**Specific Aim 5:** To explore CHC primary care providers opinions about the lung screening PN program via survey

## **II. BACKGROUND AND SIGNIFICANCE**

Though the incidence of lung cancer is similar to other common cancers such as breast and colorectal cancer, the large discrepancy in terms of mortality can be attributed in part to the widespread availability of screening and early detection for breast and colorectal cancer. The National Lung Screening Trial (NLST) sought to

evaluate screening using low-dose helical CT (LDCT) compared to chest radiography at baseline and then annually for 2 years. The study evaluated 53,439 asymptomatic participants, 55 to 74 years of age, with history of at least 30 pack years of smoking enrolled at 33 centers in the U.S. from August 2002 through April 2004. Initial results published in 2011 showed an increase in lung cancer diagnosed in participants in the LDCT group (292, 1.1%) compared with the radiography group (190, 0.7%). Importantly, more early stage lung cancers were diagnosed in the LDCT group compared to the radiology group (158 versus 70) along with similar numbers of late-stage cancers in each group. Follow up of the participants through the end of 2009 showed statistically significant relative reduction in mortality from lung cancer with low-dose CT screening of 20%.

As a result of the NLST and prior lung cancer screening trials using LDCT, the U.S. Preventive Services Task Force (USPSTF) has issued new draft guideline recommendations. The proposed screening recommendations for LDCT apply to men and women smokers or former smokers who quit in the past 15 years, without signs or symptoms of lung cancer, between the ages of 55 and 80 years, who have a 30+ pack-years of smoking. In February of 2015 Medicare announced its requirements for LDCT screening. All high risk current and former smokers as defined by USPSTF, age 55-77 are eligible for annual LDCT. Additionally, patient must receive a written order for LDCT lung screening and shared decision making visit, furnished by a physician or qualified non-physician practitioner.

The availability and coverage for LDCT screening does not mean that all eligible individuals will be screened. To improve cancer screening and follow-up in vulnerable populations, various strategies have been evaluated, including patient navigation. Implemented in 1990 by Freeman, patient navigation (PN) uses culturally and linguistically tailored outreach workers to explore barriers to cancer care and navigate patients to obtain necessary care. Several studies have shown that patient navigation can significantly improve breast and colon screening rates, follow up after abnormal results and decrease disparities in care. Currently, lung screening with LDCT has not been widely used at Massachusetts General Hospital (MGH). As a result, we have a unique opportunity to investigate how to promote screening in eligible, vulnerable patients and to prevent the creation of disparities in care.

### **III. SUBJECT SELECTION**

According to internal MGH data from 2012, 1480 patients aged 55-79 years at MGH CHCs were current smokers. Of these patients, 204 had a chest CT scan in the prior 18-months and/or had a diagnosis of lung cancer. Because of new Medicare guidelines we will only include patients that are aged 55-77 years and additionally exclude patients that providers deem ineligible for lung cancer screening. We estimate the total number of patients eligible for our interventions to be around 1200. Our experience in prior PN colorectal cancer screening interventions is that one full-time navigator assigned 400 patients will be able to reach/work with 300 patients over a 9-month period. Since our navigator will also follow-up abnormal CT results, our study will last one year. Eligible patients will be identified, randomized, and an electronic list of patients will be downloaded into an existing TopCare navigator data base. The navigators will use this system to track patients and interventions. Patients randomized to the interventions group will be recruited by navigators during their visits to the health center or over the phone. Since the navigator program is already standard of care at MGH, its expansion to include lung screening is considered part of usual care.

For Specific Aim 5, primary care physicians (PCPs) and nurse practitioners (NPs) from the community health centers with the PN program will be asked to complete a survey following the study period. There are approximately 81 PCPs and NPs who will be asked to complete the survey.

### **IV. SUBJECT ENROLLMENT**

For this study, we will use a newly developed TopCare smoking and lung screening registry. The registry uses the data from patient's EMR regarding the smoking history and imaging (most recent chest CT) and it is daily

updated. We will choose the current smokers age 55-77 from the registry who did not have chest CT in the last year receiving care at MGH health centers. We will e-mail primary care providers a list of their patients and ask them to notify us in a week if they do not want us to contact a patient and to provide a reason why they believe patient is not eligible for lung screening. Patients meeting eligibility criteria for the study according to the criteria above will be identified and randomly assigned to navigation or control group. An electronic list of patients assigned to the intervention group will be downloaded into an existing TopCare navigator data base. The navigators will use this system to track patients and record interventions. Patients randomized to the intervention group will be recruited by navigators during their visits to the health center or over the phone. Since the navigator program is already standard of care at MGH, its expansion to include lung screening is considered part of usual care.

The patients in the intervention group will be mailed a letter about the program in English or Spanish with educational materials about lung screening following randomization and prior to any contact by the PN. A week later, the PN will contact patients over the phone or in person during office visits. For patients that speak languages other than English or Spanish, this initial contact with the PN will be aided by an interpreter. The interpreter will review the recruitment letter and Fact Sheet with the patient and ask the patient if they are interested in continuing with the research study. During this initial contact, the PN will obtain a detailed history to determine if the patient is eligible for lung screening. The PN will educate patients about lung screening and explore their barriers to screening. The PN will coordinate scheduling a shared decision appointment with a provider and, whenever feasible, attend the visit with the patient. The PN will further coordinate scheduling the lung screening test if the provider and patient made that decision and navigate the patient to obtain the test. Interventions may include: reminding the patient about the test, helping with translation, insurance issues, transportation, and overcoming any other system barriers as needed. After screening, PN will review the results. If the patient has an abnormal test result, the navigator will contact the patient's primary care physician and help the patient obtain required follow-up.

As a part of lung screening, the PN will assess the patient's interest in quitting smoking. If the patient is interested in quitting, the PN will offer and help to connect the smoker to existing cessation resources in the community and CHCs and provide follow-up contacts to monitor adherence to treatments. The PN will direct smokers to the 5-call proactive telephone smoking cessation counseling provided free by the MA Quitline. The PN will use a QuitWorks fax-referral system to make the Quitline referral; by doing so, the smoker is eligible for two weeks of free nicotine patch or gum as well. The PN will also explain that pharmacologic treatment doubles quit rates when added to behavioral counseling, describe the available FDA-approved smoking cessation medications (nicotine replacement products, bupropion, and varenicline), and refer to the PCP for a recommendation and prescription. The PN will monitor patient progress by contacting the patient weekly for up to six weeks, followed by monthly follow-up until the end of the study. If a patient declines smoking cessation assistance, the PN will continue to inquire every three months if the patient has changed his/her mind about cessation and/or LDCT screening. Navigators will record information on every patient they contact and note all the interventions that were attempted.

For the patient satisfaction surveys in Specific Aim 4, patients will be contacted by telephone and asked to participate if they received PN services as part of the lung screening PN program and have contact with the navigator. We will also randomly select patients from the delayed intervention/control group to complete a satisfaction survey.

For the PCP and nurse practitioner (NP) surveys in Specific Aim 5, PCPs and NPs will be provided a paper survey at regular practice meetings by the PI of this study and asked to complete the survey. Providers that do not attend the practice meeting will receive the request to fill out the survey via interoffice mail or email.

## **V. STUDY PROCEDURE**

### **V.1. Overview**

We propose to develop, implement, and rigorously evaluate a novel lung screening patient navigator program for patients that currently smoke in five community health centers affiliated with a primary care network of a large academic hospital.

Eligible patients will include those receiving care in community health centers who are 55-77 years old and currently smoking. The intervention trial will be randomized at the patient level. In the intervention group, patients will be contacted by a culturally competent PN who will help them stop smoking and obtain lung screening. The control patients will receive usual care. The primary outcome will assess the percentage of eligible patients in intervention and control groups who had at least one chest CT during the study period. Secondary outcomes will include as-treated primary outcomes among intervention patients contacted by the patient navigator, primary outcomes stratified by language spoken, race, age, and practice site, follow-up of abnormal results, percentage of patients with tobacco treatment, and comparison of lung screening to other practices in the primary care network.

## V.2. Time Line

As depicted in **Table 1**, the work planned for **Specific Aim 1** is occurring during Study Year 1. Development of the program, hiring and training navigators, as well as organizational aspects that are necessary to permit the timely implementation and evaluation of the intervention (**Specific Aim 2**) will occur over the course of Year 2 with completion in early Year 3. The remainder of Year 3 will be devoted to outcomes evaluation, (**Specific aim 3**) analysis, and dissemination.

Task	0-4	5-8	9-12	13-16	17-20	21-24	25-28	29-32	33-36
Specific Aim 1									
Develop smokers registry									
Software development for PN									
Develop curriculum and procedure manual for PN									
Present the program at CHC PCP meetings									
Develop educational materials for patients									
Navigator training									
Specific Aim 2 and 3									
Randomization									
Baseline evaluation									
Intervention									
Outcome evaluation (at 1 year)									
Analysis & manuscript writing									
Dissemination									
Note: Lighter shaded boxes denote option for additional time if needed.									

## V.3. Patient Navigation for Lung Screening at MGH Community Health Centers (Specific Aim 1)

In the first year of our study, we are developing a patient navigator program for lung screening for eligible patients – smokers aged 55-77 years receiving care at the CHCs affiliated with MGH. This includes:

1. We will take advantage of a registry of smokers aged 55-80 years being developed for the TopCare population management system in the MGH primary care network.
2. The PI is working with medical directors of the five CHCs to give an overview of new guidelines for LDCT lung screening along with details of the planned study at provider meetings.
3. We are interviewing candidates for PN position

4. We are developing a procedure manual for the program using previously developed manuals for existing PN programs at MGH as a template.
5. We are evaluating currently available shared decision lung screening tools to use for our study
6. We will train the PN on motivational interviewing, problem solving, IT system, electronic medical record documentation as well as smoking cessation and lung screening. We will create a procedure manual with phone scripts, talking points, time frame of the calls, templates to facilitate documentation in the medical record and communication with providers. Training and supervision during the study period will be provided by PI, PN manager and MGH Chelsea HC community health director.

#### **V.4. Randomized Clinical Trial (Specific Aim 2)**

To test our hypothesis we will randomize eligible patients receiving care at CHCs to one of two study groups:

Early intervention	Usual care/delayed intervention
400 patients will receive 1:1 PN to obtain lung screening and follow-up of abnormal results, as well as smoking cessation guidance	800 patients will receive usual care during the 1-year study period. After the study period they will be offered 1:1 PN to obtain lung screening and follow-up of abnormal results as well as smoking cessation guidance

Eligibility criteria:

1. Inclusion criteria: adult patients aged 55-77 years who are current cigarette smokers (according to an algorithm using EMR data), and receive care at one of the five MGH CHCs.
2. Exclusion criteria: 1) patients who have previously received a diagnosis of lung cancer per EMR, 2) have undergone a chest CT within 18 months before enrollment, 3) are subsequently identified as having died prior to the study intervention 4) deemed by their primary care provider as not eligible for lung screening

Patients will be identified using existing electronic systems developed by the MGH Primary Care Operations Improvement (PCOI) program (Protocol # 2004P002796).

Using a newly developed TopCare smoking and lung screening registry, we will identify smokers receiving care at MGH health centers who could be eligible for lung screening. We will e-mail primary care providers a list of their patients and ask them to notify us in a week if they do not want us to contact a patient and to provide a reason why they believe patient is not eligible for lung screening. The eligible patients will then be randomly allocated to the intervention or usual care groups. Patients randomly assigned to the intervention group will be eligible for PN, while patients randomly assigned to the control will receive usual care and be eligible for navigation after the one year period.

Patient navigator intervention:

PN program delivery: A letter about the program with lung screening educational materials used in usual clinical practice will be mailed to eligible patients. A week later, the PN will contact patients over the phone or in person during office visits. The letters will be sent in stages. First, PN will use TopCare IT system to identify patients who have appointment scheduled and send letters/contact them prior to their appointments. Patients who do not have appointments scheduled will be contacted in stages so that during the first 6 months of the study all eligible patients receive a letter and at least one phone call attempt from PN. During the initial contact, the PN will obtain detailed history to determine if patient is eligible for lung screening. The PN will educate patients about lung screening and explore any barriers to screening. If the patient is interested in screening, the PN will coordinate scheduling a shared decision-making appointment with a provider and, whenever feasible, attend the visit with the patient. The PN will further coordinate scheduling the CT scan if the provider and patient made that decision and navigate the patient to obtain the test. Further interventions may include:

reminding the patient about the test, helping with translation, insurance issues, transportation, and overcoming any other system barriers as needed. After screening, the PN will review the results. If the patient has an abnormal test result, the navigator will contact the patient's primary care physician and help the patient obtain required follow-up.

As a part of lung screening, the PN will assess the patient's interest in quitting smoking and provide motivational message about the importance of quitting despite having lung screening. If the patient is interested in quitting, the PN will offer and help to connect the smoker to existing cessation resources in the community and CHCs and provide follow-up contacts to monitor adherence to treatments. The PN will refer smokers to the 5-call proactive telephone smoking cessation counseling provided free by the MA Quitline. The PN will use a QuitWorks fax-referral system to make the Quitline referral; by doing so, the smoker is eligible for four weeks of free nicotine patch or gum as well. The PN will also offer refer to in-person counseling from CHC tobacco coach. Additionally, the PN will explain that pharmacologic treatment doubles quit rates when added to behavioral counseling, describe the available FDA-approved smoking cessation medications, and refer to the PCP for a recommendation and prescription of bupropion or varenicline, which are available only by prescription. The PN will monitor patient progress by trying to contact the patient up to 3 times over 1-2 months period to make sure that patient received smoking cessation intervention referred to. Navigator will record information on every patient they contact and note all the interventions that were done.

#### **V.5. Prospective Data Collection for Disparities in LDCT and Smoking Cessation (Specific Aim 3)**

To determine whether the patient navigator program maintained equity in obtaining lung screening among smokers from CHCs compared to smokers from other MGH primary care practices, we will examine lung screening rates in the two study populations in the year prior to the intervention and after the 1-year intervention period. Eligibility criteria are the same as in Specific Aim 2, except the analysis will include patients in all MGH affiliated primary care practices stratified by CHC or other.

Lung screening rates prior to and after the 1-year intervention period will be compared among eligible patients receiving care at one of the five MGH CHCs (all patients and subgroup of those who received the early intervention) and eligible patients from all other MGH practices.

Patients will be identified using existing electronic systems developed by the MGH PCOI program (Protocol # 2004P002796).).

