### Outcome measure

Percentage of current smokers aged 55-77 years at baseline who have a chest CT in the subsequent 1 year, comparing patients receiving care at CHCs with patients from all other practices within the MGH primary care network.

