#### **AIM3:**

We will use a chi-square test to compare lung screening rates between patients receiving care at CHCs to patients from other practices within the MGH primary care network during the one-year study period.

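### Aim 3 carries over the provider-judged exclusion, but the plan describes collecting that judgement only for health-center patients, so the equity contrast may be filtered on one side

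*Combined protocol and SAP*

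**What the plan says.** Section V.5 sets the Aim 3 population by reference to Aim 2: "Eligibility criteria are the same as in Specific Aim 2, except the analysis will include patients in all MGH affiliated primary care practices". The fourth Aim 2 exclusion in section V.4 covers patients "deemed by their primary care provider as not eligible for lung screening".

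Section V.4 explains how that judgement is obtained. It starts from the smoking registry, from which "we will identify smokers receiving care at MGH health centers who could be eligible for lung screening". The next step is the provider query: "We will e-mail primary care providers a list of their patients and ask them to notify us in a week". Providers name the patients they do not want contacted and say why they think them ineligible. Section IV describes the same step, also for health-center patients. Randomization follows.

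For Aim 3, section V.5 says only: "Patients will be identified using existing electronic systems developed by the MGH PCOI program". It mentions no provider query. It asks for CT rates in the year before and the year after the start of the intervention. The other practices are to be compared with all CHC patients and with the subgroup who received the early intervention.

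The Aim 3 outcome measure is given as "Percentage of current smokers aged 55-77 years at baseline who have a chest CT in the subsequent 1 year", with no exclusions listed for either group. The Aim 3 analysis in section VI.3 reads: "We will use a chi-square test to compare lung screening rates between patients receiving care at CHCs to patients from other practices". No adjustment is planned.

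**The concern.** The two sides of Aim 3 need the same filter. Exclusion 4 is not a field that can be read from the electronic medical record (EMR). It exists only where a provider was asked, and the plan describes asking only about health-center patients. An analyst who applies the V.5 rule to the data the plan collects would remove opted-out patients from the CHC denominator and leave their counterparts in the comparison denominator.

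Part of any CHC-versus-other difference, or of its absence, could then come from the filter. If opted-out patients are seldom scanned, removing them raises the CHC rate and equity looks better maintained than it is. If they are sicker and are scanned more often, which is possible because any chest CT counts, removing them lowers the CHC rate. The Aim 3 conclusion is a direct reading of this contrast, so its denominator should not be left to interpretation.

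**Working it through.** **Inputs from the documents**
- CHC current smokers aged 55-79 in 2012: 1480 (section III).
- Of these, with a chest CT in the prior 18 months and/or lung cancer: 204 (section III).
- Estimated eligible after the age limit of 77 and the provider exclusion: about 1200 (section III).
- Early-intervention group: 400, with 800 in usual care (section V.4).
- Hypothesized effect: 5%, read here as absolute percentage points (section VI.4).

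**The plan's own figure.** 1480 - 204 = 1276, which is the total used in section VI.4. Aim 3 itself has no stated sample size, margin or power. The 88% power in section VI.4 is for Aim 2 and does not bear on this point.

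**Share filtered.** 1276 - 1200 = about 76, and 76/1276 = 6.0%. The 76 also includes patients aged 78-79, so 6.0% is an upper bound on the planned provider opt-outs. The 1200 is itself approximate.

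**Size of the artefact.** Let f be the share that providers would opt out, r the CT rate in patients who would be retained, and q the CT rate in patients who would be opted out. Suppose both populations are truly alike and only the CHC side is filtered.
- CHC observed rate = r
- Other-practice observed rate = (1 - f)r + fq
- Spurious CHC-minus-other gap = f(r - q)

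The documents give neither r nor q. With f = 6.0% and r = 10% (assumed):

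| CT rate in opted-out patients (assumed) | Other-practice rate | Spurious gap |
|---|---|---|
| 0% | 9.4% | +0.6 points |
| 10% | 10.0% | 0 |
| 30% | 11.2% | -1.2 points |

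Over r = 5% to 20% and q from 0 to 2r, the gap at f = 6.0% runs from -1.2 to +1.2 points. If the actual opt-out share were 20% (an assumption well above the planning figure), the same grid gives -4 to +4 points.

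**Scale.** Only 400 of about 1200 CHC patients are navigated in the study year, so a 5-point effect moves the all-CHC rate by 5 x 400/1200 = 1.7 points. An artefact of 0.6 to 1.2 points is roughly one third to seven tenths of that.

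**Early-intervention subgroup.** Section V.4 randomizes after the opt-out, so this subgroup is provider-filtered however V.5 is read. Its contrast with other practices is filtered on one side unless those practices receive an equivalent query.

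**The two years.** Section V.5 also needs a prior-year rate. Exclusion 2 removes patients with a chest CT within 18 months before enrollment. If that look-back is anchored at enrollment, the prior-year rate is zero by construction. The Aim 2 criteria therefore cannot simply be carried over; they have to be applied at the start of each year compared. The look-back also needs one value, since section IV gives one year and section V.4 gives 18 months.

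**The case against.** The strongest reply is that no sentence says exclusion 4 is applied to CHC patients only. V.5 calls the criteria the same for all practices, and the outcome measure names no exclusion for either group, so each text taken literally is symmetric. V.4 also begins with the same electronic identification and then adds the provider query, so V.5 does not rule out a query elsewhere. This stands: one-sided filtering is an inference from what the plan describes collecting. It does not rescue the early-intervention contrast, and it leaves V.5 requiring a judgement that the plan never says it will collect in other practices.

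A second reply is that the effect is small and its sign unknown. This also stands at the planned opt-out share.

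A third is that the one-line outcome measure is shorthand. The Aim 2 primary outcome in VI.1 omits the exclusions too, and Specific Aim 3 speaks of eligible smokers on both sides. That is probably right. Stating the exclusions there would still remove the ambiguity.

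A fourth is that running the same provider query in all practices would restore symmetry and keep the V.5 criteria as written. It would, but it needs a new data-collection step.

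A reader might go further in three ways that the documents do not support:
- **That the bias is established.** It is conditional on how V.5 is carried out, and it is zero if opted-out patients are scanned at the same rate.
- **That exclusion 3 (death before the intervention) has no meaning in other practices.** Death before a common calendar date can be ascertained anywhere.
- **That dropping all exclusions shows a large bias.** Adding back the 204/1480 = 13.8% with a recent CT or lung cancer, at an assumed 30-60% CT rate, moves 10% to between 0.862 x 10% + 0.138 x 30% = 12.8% and 0.862 x 10% + 0.138 x 60% = 16.9%. The outcome measure would apply this to both groups, so it shifts the level of both rates and does not measure a difference between them.

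**Conclusion.** The concern holds as a gap in the definition of the Aim 3 denominator that could bias the contrast; it does not hold as a demonstrated bias. V.5 imports a provider judgement that the plan describes obtaining only for health-center patients, and the unadjusted test would not correct for filtering on one side. At the planning figure of at most about 6% opted out, the artefact is about a point in either direction. That size rests on assumed CT rates, on the 2012 counts, and on the two populations being otherwise alike. It would grow if providers opted out more patients than planned. The point is worth fixing because the change is cheap and the all-CHC effect that Aim 3 could show is itself small. It concerns a non-randomized secondary comparison and leaves the randomized primary comparison untouched.

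**What to change.** In V.5 and in the Aim 3 outcome measure, state one denominator using only criteria obtainable identically from the EMR in both groups:
- age 55-77;
- current smoker;
- no lung cancer diagnosis;
- no chest CT within one stated look-back;
- alive at a common index date.

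Apply these at the start of each year being compared. Do not apply exclusion 4 in the main Aim 3 comparison, so that opted-out CHC patients return to the denominator. Report how many were opted out, show the provider-filtered CHC rate as a sensitivity result, and label the early-intervention subgroup contrast as provider-filtered.

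The cost is wording and a small amount of extra analysis on data that the EMR and registry should already hold. The downside is minor: the CHC rate will include some patients whose provider judged them unsuitable, as the comparison group already does when no provider is asked.
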